Experimental Therapeutics/Psychiatry

Within the division/department, what Center or group are you affiliated with, if any?

Silvio O. Conte Center for Schizophrenia Research

Unaffiliated Personnel

List investigators, if any, who will be participating in this protocol but are not affiliated with New York State Psychiatric Institute or Columbia University. Provide: Full Name, Degrees and Affiliation.

[name].

Application for Continuation of Research

Status

Current Status of Study:

All research interventions were completed. Only data analysis is ongoing.

Summary of Experiences to Date

Please provide a summary of scientific progress of the study and the experience of research participants, to date. This requirement is designed to allow for the investigator and the IRB to reassess the study's risks and benefits in terms of developments in the field, changing practice patterns, and new IRB policies and procedures.

Study has been completed. Data analysis continues for an R61-R33 application. A manuscript has been submitted to Biological Psychiatry and will be presented at ACNP 2018.

Funding

Have there been any changes in funding status since the prior approval?

No

Have the principal investigator and other investigators made all required disclosures of financial interest in the study sponsor/product?

Yes

Summary

Have there been any study findings, recent literature, or untoward events occurring here or at other sites in the past year which might affect the analysis of the safety, risks or benefits of study participation?

No

Have there been any serious adverse events (serious and/or unanticipated problems involving risks to subjects or others at this site which occurred in the past year)?

No

Have all study staff with a significant role in the design or implementation of the human subject components of this study received required training in human research subject protections?

No

Is the study covered by a certificate of confidentiality?

Yes

Certificate expiration date (mm/dd/yyyy)

12/31/2021

Overall Progress

Approved sample size

120

Total number of participants enrolled to date

75

Number of participants who have completed the study to date

56

Have there been any significant deviations from the anticipated study recruitment, retention or completion estimates?

No

Comments / additional information

Study enrollment is ended.

Sample Demographics

Specify population

schizophrenia

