Total number of participants enrolled from this population to date

65

Gender, Racial and Ethnic Breakdown

Caucasian: 26

African-American: 36

Hispanic: 9

Asian: 1

Other: 3

Male: 56

Female: 19

Summary of Current Year's Enrollment and Drop-out

Number of participants who signed consent in the past year

0

Did the investigator withdraw participants from the study?

No

Did participants decide to discontinue study involvement?

No

Procedures

To create the protocol summary form, first indicate if this research will include any of the following procedures

- ✓ Psychiatric Assessment
- ✓ Neuropsychological Evaluation
- ✓ Collection of Biological Specimens
- ✓ Use of Placebo or Sham Treatment
- ✓ MRI
- ✓ Use of Investigational Drug or Device

Population

Indicate which of the following populations will be included in this research

- ✓ Adults who may have impaired decision-making ability
- ✓ Medically and Psychiatrically Healthy Subjects
- ✓ Adults
- ✓ Adults over 50
- ✓ Individuals with Psychosis

Research Support/Funding

Will an existing internal account be used to support the project?

No

Is the project externally funded or is external funding planned?

Yes

Select the number of external sources of funding that will be applicable to this study

2

Funding Source #1

Is the PI of the grant/contract the same as the PI of the IRB protocol?

Yes

Select one of the following

The grant/contract is currently funded

Source of Funding

Foundation

Sponsor

Stanley Medical Research Institute (SMRI)

Select one of the following

Multicenter(NYSPI is the lead site)

Business Office

CU

Does the grant/contract involve a subcontract?

No

Funding Source #2

Is the PI of the grant/contract the same as the PI of the IRB protocol?

Yes

Select one of the following

The grant/contract is currently funded

Source of Funding

Federal

Institute/Agency

NIMH

Grant Name

Columbia Conte Center

Grant Number

P50 MH086385

Select one of the following

Multicenter(NYSPI is the lead site)

Business Office

CU

Does the grant/contract involve a subcontract?

No

Study Location

Indicate if the research is/will be conducted at any of the following

✓ NYSPI

This protocol describes research conducted by the PI at other facilities/locations

No

Lay Summary of Proposed Research

Lay Summary of Proposed Research

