Document Date: December 17, 2018

**Statistical analysis:** The prespecified primary behavioral endpoint was percent change across AHRS items after the five-day treatment conducted using a repeated-measures MANCOVA (rmMANCOVA) with group status as a between-subjects factor and time following randomization (one week and one month) and item (7 individual items) included as within-subject factors. In pre-specified analyses, only baseline AHRS score was used as a covariate. However, higher chlorpromazine equivalents (CPZE)  correlated significantly with higher baseline AHRS total ( $r=0.22$ ,  $p=0.04$ ) and PANSS P3 ( $r=0.30$ ,  $p=0.005$ ) scores, justifying its inclusion as an additional covariate for all analysis. Neither baseline AHRS or CPZE differed significantly between groups.

1. Woods SW. Chlorpromazine equivalent doses for the newer atypical antipsychotics. *J Clin Psychiatry* 2003; **64**(6): 663-7.

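### The SAP adds CPZE to the prespecified covariate set because of two correlations seen in the data; their sample is not stated, and two-sided they imply 82–91 patients, which matches no count in the documents

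*SAP*

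**What the plan says.** The SAP is one paragraph, Statistical analysis, dated December 17, 2018. The primary endpoint is percentage change in AHRS items, analysed by repeated-measures MANCOVA. The SAP states that baseline AHRS was the sole covariate in the prespecified analyses. It then reports that higher CPZE "correlated significantly with higher baseline AHRS total" (r=0.22, p=0.04) and with higher PANSS P3 (r=0.30, p=0.005), "justifying its inclusion as an additional covariate for all analysis". No other reason is given. The SAP does not state the number of patients, the sites, the analysis set, the type of correlation or whether the tests are one- or two-sided.

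The counts come from the protocol's continuation record:

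- Overall Progress: "Total number of participants enrolled to date", 75; "Number of participants who have completed the study to date", 56; and the comment "Study enrollment is ended".
- Sample Demographics, for schizophrenia: "Total number of participants enrolled from this population to date", 65.
- Research Support/Funding: both grants carry the marking "Multicenter(NYSPI is the lead site".
- Study Location: only NYSPI is ticked, and the item "This protocol describes research conducted by the PI at other facilities/locations" is answered No.

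**The concern.** A correlation and its p-value together determine the sample size, up to rounding and sidedness. Here they point to more patients than the protocol records, so a reader cannot tell whose data led to the change of model. This matters because the two correlations are the whole case for altering a prespecified primary analysis, and the record describes interventions as finished and a manuscript as already submitted.

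The sample also matters for relevance. Under the protocol's Comparison Samples sections, AH- patients are rated on AHRS and PANSS but are not randomised. Their exclusion criterion (mean AHRS item score above 0) would put them at or near zero on the AHRS. If they were included, the correlation could reflect group membership and would say little about a covariate for the active-versus-sham comparison.

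**Working it through.** **Inputs.** From the SAP: r=0.22 with p=0.04, and r=0.30 with p=0.005. From the protocol: n=75, 65 and 56. Assumption: Pearson correlation, two-sided, with one-sided also tried. Rounding limits: r ±0.005; p ±0.005 for the AHRS pair and ±0.0005 for the P3 pair.

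**Formula.** t = r·√(n−2) / √(1−r²), on n−2 degrees of freedom.

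**1. Do the printed p-values reproduce at the recorded sizes?** For r=0.22, √(1−0.0484) = 0.9755. For r=0.30, √(1−0.09) = 0.9539.

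| n | t, r=0.22 | two-sided p | t, r=0.30 | two-sided p |
|---|---|---|---|---|
| 75 | 0.22×8.544/0.9755 = 1.93 | 0.058 | 0.30×8.544/0.9539 = 2.69 | 0.009 |
| 65 | 0.22×7.937/0.9755 = 1.79 | 0.078 | 0.30×7.937/0.9539 = 2.50 | 0.015 |
| 56 | 0.22×7.348/0.9755 = 1.66 | 0.10 | 0.30×7.348/0.9539 = 2.31 | 0.025 |

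Neither printed p-value appears at any of the three sizes. Rounding does not rescue the AHRS figure: r=0.225 gives p=0.052 at n=75 and 0.072 at n=65. The smallest |r| significant at 5% two-sided is 0.227 at n=75 and 0.244 at n=65. The P3 correlation stays below 0.05 throughout.

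**2. What n do the printed pairs imply, two-sided?**

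- AHRS pair: best fit n=88; rounding range 80–96.
- P3 pair: best fit n=86; rounding range 82–91.
- Common to both: 82–91 (Fisher's z gives 81–90).

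As a check at n=86: r=0.22 gives t = 0.22×9.165/0.9755 = 2.07, p=0.042; r=0.30 gives t = 0.30×9.165/0.9539 = 2.88, p=0.0050. Both round to the printed values.

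**3. One-sided.**

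- AHRS pair: best fit n=64; range 58–71.
- P3 pair: best fit n=73; range 69–77.
- Common to both: 69–71, which is below 75 but above 65.

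This overlap exists only if rounding in r is used. With r taken exactly as printed, the one-sided ranges are 61–68 and 72–74 and do not meet, whereas the two-sided ranges (84–92 and 85–88) share 85–88.

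**4. How firm are the recorded counts?** The sex counts printed under the 65 sum to 56+19 = 75, and the race and ethnicity counts to 26+36+9+1+3 = 75, so the 65 does not match its own breakdown. No AH+ count is given anywhere.

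**The case against.** The strongest reply is that 75 and 65 may be the wrong yardstick. Both grants are marked multicentre with NYSPI as lead site, and the record says it does not cover other locations, so its counts may be one site's share. Two separate pairs agreeing on nearly the same n looks more like one real sample than a misprint. This stands: a pooled sample of about 86 would make the printed p-values correct. It does not remove the need to name the sample.

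Three stronger readings are tempting, and the documents support none of them:

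- *The printed figures are wrong.* Pooling or one-sided testing could explain them, and nothing in the documents excludes either.
- *The justification for CPZE collapses.* The SAP gives two correlations, and the P3 one stays below 0.05 at every recorded size.
- *The AHRS correlation would disappear on recomputation.* The p-values of 0.058, 0.078 and 0.10 hold r at 0.22. In a different set of patients r could be larger or smaller.

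It can also be said that the n puzzle does not by itself decide which model is primary, and that the SAP openly discloses the prespecified covariate set. Both points are fair. The case for restoring that model rests on the SAP's own account that CPZE was added after correlations were seen, which holds at any n.

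**Conclusion.** The concern holds in a limited form. By the SAP's own account, a prespecified covariate set was enlarged for all analyses because of correlations observed in the data, and those correlations cannot be traced to a stated sample. Assuming two-sided Pearson tests, they imply 82–91 patients, against 75 enrolled, 65 under schizophrenia and 56 completers. If r=0.22 held at the recorded sizes, the AHRS half of the justification would miss 5% significance; the P3 half would not. Whether the explanation is pooled sites, one-sided tests, non-randomised patients or an error cannot be decided from the documents. The effect of the CPZE adjustment on the treatment comparison is also unknown, since the SAP reports neither model's result.

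**What to change.** Keep the prespecified model, with baseline AHRS as the only covariate, as the primary analysis, and report the CPZE-adjusted model as a sensitivity analysis. Recompute both correlations in the randomised AH+ set used for the primary model, and state the n, the contributing sites, the type of correlation and the sidedness. If the sample is pooled across sites, say so and give the count per site.

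The cost is two correlations and a few sentences in the SAP. The CPZE-adjusted result loses primary status, and any gain in precision from CPZE appears only in the sensitivity analysis.

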(stimulate) or decrease (inhibit) activity in underlying brain regions. It has been reported that applying inhibitory currents over left auditory regions for 20 min per day over 5 consecutive days leads to significant, long-lasting reductions in auditory hallucinations (6). The present study seeks to replicate this finding and will utilize MRI measures of brain activity and metabolism and behavioral assessments to understand the underlying mechanisms.

Specific Aims and Hypotheses

Specific Aims and Hypotheses

The aim of this study is to evaluate the effects on schizophrenia symptoms of tDCS applied with cathodal (inhibitory) electrode over the left temporo-parietal junction and anodal (excitatory) electrode over the left dorsolateral prefrontal cortex.

Our specific hypotheses are:

1. In comparison to sham, active tDCS treatment will decrease the severity of refractory auditory hallucinations in patients with schizophrenia
2. In comparison to sham, active tDCS treatment will decrease the severity of negative schizophrenia symptoms
3. In comparison to sham, active tDCS treatment will normalize auditory function as reflected in stronger prediction error signals in the auditory cortex during the auditory discrimination task and decreased baseline activity in this region.
4. In comparison to sham, active tDCS treatment will normalize auditory function as reflected in reduced cerebral blood flow in auditory cortex and normalized metabolism.
5. Symptom alleviation following active tDCS treatment will be maintained over the course of 3 months

The two control groups (AVH- and healthy controls) will serve as comparison groups for specific AIM 3 and 4 only.

Description of Subject Population

Sample #1

Specify subject population

Schizophrenia patients with auditory hallucinations

Number of completers required to accomplish study aims

60

Projected number of subjects who will be enrolled to obtain required number of completers

75

Age range of subject population

18-55

Sample #2

Specify subject population

Schizophrenia patients without auditory hallucinations

Number of completers required to accomplish study aims

20

Projected number of subjects who will be enrolled to obtain required number of completers

30

Age range of subject population

18-55

Sample #3

Specify subject population

Non-clinical control participants

Number of completers required to accomplish study aims

20

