Projected number of subjects who will be enrolled to obtain required number of completers

30

Age range of subject population

18-55

Gender, Racial and Ethnic Breakdown

Expected racial breakdown is approximately 50% Caucasian, 16% African-American, 16% Hispanic, 16% Asian, and 2% other. Expected gender ratio is 50% male and 50% female.

Description of subject population

60 patients between the ages of 18 and 55 with a SCID diagnosis of schizophrenia or schizoaffective disorder will be enrolled in the study. All participants will exhibit refractory auditory verbal hallucinations, defined as the persistence of daily hallucinations without remission despite antipsychotic medication at adequate dosage for at least 3 months.

In addition to the primary intervention group, two comparison groups will be studied:

1. A group of patients with minimal or no auditory hallucinations (AH-) (n=20); and
2. A group of non-clinical healthy volunteers (n=20)

These subjects will be tested using a subset of the baseline assessment battery used with AH+ patients, but will not receive tDCS or repeat assessments.

All patients will be receiving antipsychotic medication at the time of study entry. Patients will remain on their present dose of antipsychotic medication throughout the treatment interval.

All participants will receive a physical examination and medical history evaluation in order to rule out disorders that might increase risks associated with tDCS, a urine toxicology screen to rule out illicit drug abuse, and a pregnancy test for women of childbearing capacity. After passing all screening criteria, participants may be removed from the study if they do not comply with study procedures, if there is a

change in their medical status, or if an adverse event has occurred.

Recruitment Procedures

Describe settings where recruitment will occur

Patients with schizophrenia will be recruited through the Lieber Schizophrenia Research Clinic and the community by our staff, all of whom will have undergone CITI and HIPAA training. Healthy controls will be recruited from the community.

How and by whom will subjects be approached and/or recruited?

Patients will be recruited from the Lieber Schizophrenia Research Clinic as follows:

1. Clinical psychiatrists and psychologists of each service will be informed about the study.

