An M.D. who is unaffiliated but familiar with the study will ask potential participants who have been diagnosed with schizophrenia questions about the study procedures and associated risks in order to determine whether the patient understands the study and has the capacity to provide consent.

Study Procedures

Describe the procedures required for this study

Overview

AH + Sample

The treatment portion of this study will follow a double-blind parallel arm design in which patients, raters and investigators will be blinded with respect to condition assignment. All personnel will have undergone HIPAA and CITI training. Following a clinical evaluation to determine eligibility, patients will be assigned to either the active or the sham condition. In the active condition, patients will receive cathodal stimulation to the left temporo-parietal junction and anodal stimulation to the left dorsolateral prefrontal cortex at 2mA X 20 min in each session. In the sham condition, electrodes will be placed over the same regions, but current will be applied under a “sham” approach in which currents are initially ramped up over 30 s as in the active condition, but then immediately ramped down. Prior experience has shown that subjects do not distinguish the active and sham conditions. Patients will participate in two daily sessions of 20 minutes each for 5 consecutive weekdays. Auditory hallucinations as determined by the Auditory Hallucinations Rating Scale (AHRS) and the five dimensions of schizophrenia symptoms assessed in the Positive and Negative Syndrome Scale (PANSS) will be assessed at baseline, immediately following the final treatment, and at 1- and 3-month follow-up timepoints. AHRS will be repeated prior to first treatment session. All subjects will be assessed prior to and following initiation of 5-d treatment period using a neurophysiological battery sensitive to auditory dysfunction in schizophrenia, and neuropsychological tests of auditory and general neurocognitive impairment. The neurophysiological impact of tDCS will be assessed by MRI procedures described below at baseline and immediately following the final treatment. MRI sessions are optional for AVH+ patients.

Comparison Samples

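### The SAP replaces the prespecified baseline-only primary model with a CPZE-adjusted one because of correlations seen in the trial data, and does not promise to report the prespecified result

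*SAP*

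**What the plan says.** The SAP's single section, Statistical analysis, defines the primary as percent change across the seven AHRS items at one week and one month, compared between groups by rmMANCOVA. On covariates it states: "In pre-specified analyses, only baseline AHRS score was used as a covariate". The next sentence turns on a contrast. Higher CPZE "correlated significantly with higher baseline AHRS total" (r = 0.22, p = 0.04) and with higher PANSS P3 (r = 0.30, p = 0.005), and the SAP presents this as "justifying its inclusion as an additional covariate for all analysis". It adds: "Neither baseline AHRS or CPZE differed significantly between groups".

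The SAP does not say that the baseline-only model will be reported, which of the two models is now primary, when CPZE was added relative to unblinding, or when CPZE was measured. The protocol sections supplied contain no statistical section and do not mention CPZE. On dose stability, the protocol (Description of subject population) says: "Patients will remain on their present dose of antipsychotic medication throughout the treatment interval".

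**The concern.** A covariate set fixed in advance protects the primary test from choices made with data in hand. Here the SAP itself says the set was fixed and then changed because of trial data, and the change reaches every analysis, including the primary.

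The stated reason does not support the change for that analysis. A covariate earns its place by predicting the outcome given what is already in the model. Baseline AHRS is already there, so its correlation with CPZE does not show what CPZE adds. PANSS P3 is not the primary outcome. Chance imbalance is not the reason either, since the SAP reports no significant group difference in CPZE. The P3 correlation may bear more on the PANSS analyses, but no CPZE–outcome association is given for those.

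At stake is whether a reader can see if the primary conclusion depends on the added covariate. Adjustment for CPZE measured at entry does not itself bias the treatment comparison.

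**Working it through.** **Inputs from the documents.** Prespecified covariate: baseline AHRS only. Added covariate: CPZE. Correlations: 0.22 (p = 0.04) and 0.30 (p = 0.005). Repeated measures: 7 items × 2 times = 14 cells per patient. The protocol's continuation report gives 56 completers, 65 enrolled with schizophrenia and 75 enrolled overall; it does not give the number randomised.

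**Assumptions.** Two-sided 0.05 (the documents state no alpha); 1:1 allocation; n = 56, 65, 75 or 86, where 86 is about the n that the printed correlations imply; partial correlation ρ of CPZE with outcome given baseline AHRS of 0, 0.1, 0.2 or 0.3, because the SAP reports none. With complete data the group main-effect F in the repeated-measures model equals the ANCOVA F on each patient's mean over the 14 cells. A single-outcome ANCOVA therefore suffices for that term, but does not cover group-by-time or group-by-item terms.

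**Step 1: the printed correlations.** t = r·√[(n−2)/(1−r²)]. At n = 86:
- r = 0.22: t = 0.22 × √(84/0.9516) = 2.07, two-sided p = 0.042.
- r = 0.30: t = 0.30 × √(84/0.91) = 2.88, two-sided p = 0.005.

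Allowing for rounding, the two pairs agree on n = 82–91 two-sided (80–96 and 82–91) or n = 69–71 one-sided (58–71 and 69–77). The SAP gives neither N nor sidedness. With the 75 enrolled overall, two-sided p would be 0.058 and 0.009. This is a side query, not a demonstrated error: the protocol lists the funding as multicenter.

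**Step 2: type I error** (20,000 null trials per setting, Monte Carlo error about ±0.3 points):
- baseline-only model fixed in advance: 4.7–5.2%
- CPZE model fixed in advance: 4.8–5.2%
- CPZE added only if its correlation with baseline AHRS has p < 0.05: 4.8–5.2% (the rule fires in 37–54% of trials)
- CPZE added if correlated with baseline AHRS or P3: 4.8–5.2% (P3 taken as a baseline value, with an assumed correlation of 0.5 with AHRS)
- the more favourable of the two models chosen after seeing results: first row of the table

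**Step 3: how far the two models can differ.**

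| | ρ = 0 | 0.1 | 0.2 | 0.3 |
|---|---|---|---|---|
| Type I error, better of two | 5.5% | 5.5–5.9% | 5.7–6.0% | 6.3–6.5% |
| SD of difference between estimates, in standard errors | 0.11–0.14 | 0.15–0.17 | 0.23–0.24 | 0.34 |
| Opposite sides of p = 0.05 at 48–52% power (n = 56 and 86) | 2.8–3.7% | 3.9–4.6% | 6.9–7.2% | 9.8–10.3% |
| Standard error, baseline-only ÷ CPZE model | 0.991–0.994 | 0.996–0.999 | 1.012–1.015 | 1.040–1.043 |

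Two approximations confirm the simulated rows.
- SD of the difference ≈ √[ρ²/(1−ρ²) + 1/(n−4)]. At ρ = 0.3: √(0.0989 + 1/82) = 0.33 for n = 86 and √(0.0989 + 1/52) = 0.34 for n = 56. At ρ = 0: √(1/82) = 0.11 and √(1/52) = 0.14.
- Standard error ratio ≈ √[1/(1−ρ²)] × (1 − 1/(2n)). At ρ = 0.3: 1.048 × 0.991 = 1.039 for n = 56 and 1.048 × 0.994 = 1.042 for n = 86.

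Pushing ρ to 0.5 (n = 60 and 86) raises the better-of-two error to 7.0–7.7%.

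**Step 4: timing.** The SAP carries a document date of 17 December 2018. The protocol's undated continuation report says interventions were complete, analysis was continuing and a manuscript had been submitted. These facts neither show nor exclude a decision taken blind.

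**The case against.** The strongest reply is that little harm follows. The departure is openly disclosed, the trigger is a correlation with baseline scores and not a treatment result, and an entry-CPZE-adjusted test is valid in itself. All of that stands, and nothing in the documents shows that treatment results drove the change.

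It can also be said that the SAP only calls CPZE additional, and that its past tense leaves room for the baseline-only model having been run. That is possible. But the added covariate applies to every analysis, and nothing commits the sponsor to showing the other model. If it was run, reporting it costs nothing.

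A technical point is sound: the two estimates differ through chance imbalance in CPZE, and the SAP reports none that is significant. Conditioning on that balance lowers the SD of the difference to 0.10–0.29 standard errors, disagreement near 50% power to 2.7–9.6%, and better-of-two error to about 5.2–6.2%. The reductions are small. Under the null the models disagree in only about 1–3% of trials, so the larger figure belongs to a trial near the significance boundary.

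Finally, the SAP pairs CPZE with baseline AHRS, and the inclusion criteria for hallucinating patients require more than four weeks of stable antipsychotic medication, so an entry value is the natural reading. That is fair. The point still needs a sentence, because the protocol fixes dose only over the treatment interval while the primary runs to one month.

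**Conclusion.** The concern holds and should be fixed. The primary model was changed with trial data in hand, for a reason that does not show CPZE predicts the primary outcome, and the plan does not undertake to show the prespecified result.

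The size is modest. There is no bias from an entry value of CPZE, and no type I inflation under the reason given. The error is 5.5–6.5% only in the unsupported worst case of choosing after seeing results. What is lost is the ability to check that the conclusion survives: about 3–10% of trials near 50% power would change verdict between the models.

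These magnitudes rest on assumed n of 56–86, assumed ρ of 0–0.3, complete data and the group main effect. The SAP does not say which model term is the primary test. The reporting gap itself rests on the SAP's text alone and does not depend on these assumptions.

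**What to change.** In the SAP's Statistical analysis section, state: *The primary conclusion is drawn from the rmMANCOVA with baseline AHRS as the only covariate. The same model with CPZE at study entry added is a post hoc sensitivity analysis and is reported beside it whatever its result.*

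Then:
- reword the justification so that the two correlations are given as the post hoc reason for that sensitivity analysis;
- state when CPZE was added relative to unblinding;
- state when the CPZE value was taken, and use the entry value;
- as a side query, give the N and sidedness behind the two correlations.

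The cost is SAP wording and one extra model run. If CPZE is prognostic, the baseline-only primary has a standard error larger by about 1.2–1.5% at ρ = 0.2 and about 4% at ρ = 0.3. If CPZE is not prognostic, the standard error is 0.6–0.9% smaller and nothing is lost.
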